### 6.7.2. Secondary Endpoints

Secondary comparisons of interest are the mean change from baseline to Week 16 for

- total number of abscesses and inflammatory nodules (AN count), and
- Skin Pain – HS NRS.

The Skin Pain – HS Numeric Rating Scale (NRS) is a patient-administered, single-question, 11-point horizontal scale anchored at 0 and 10, with 0 representing “no pain” and 10 representing “pain as bad as I can imagine.” The recall period is 7 days.

An analysis of covariance (ANCOVA) model with proper link function will be used for analysis of these secondary endpoints on the mITT and PPS population. The AN count is a count data and we will use log transformation as the link function.

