9.4.3. Secondary Endpoints

Secondary comparisons of interest are the mean change from baseline to Week 16 for

- total number of abscesses and inflammatory nodules (AN count), and
- Skin Pain HS NRS.

An analysis of covariance (ANCOVA) model will be used for analysis of these secondary endpoints.

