9.4.4.1. Patient-Reported Outcomes

Categorical variables will be analyzed using logistic regression analyses, whereas mixed-effects model of repeated measures (MMRM) will be the primary method of analysis for continuous endpoints. The analyses will be based on the mITT population, unless otherwise specified.

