### **6.3.3. Analysis Methods**

The main analysis of categorical efficacy variables and health outcomes variables will use a logistic regression analysis with treatment group in the model. The p-value and 100(1-alpha)% CI for the odds ratio from the logistic regression model are used for primary statistical inference. The difference in percentages and 100(1-alpha)% CI of the difference in percentages using the Newcombe-Wilson without continuity correction will be reported. The p-value from the Fisher's exact test will also be produced as a secondary analysis.

The main analysis for all continuous efficacy and health outcomes variables will use mixed model repeated measures (MMRM) analysis. The model will include treatment, region, baseline disease severity, visit, and treatment-by-visit-interaction as fixed categorical effects and baseline and baseline-by-visit-interaction as fixed continuous effects. An unstructured (co)variance structure will be used to model the between- and within-patient errors. If this analysis fails to converge, the heterogeneous autoregressive [ARH(1)], followed by the heterogeneous compound symmetry (CSH), followed by the heterogeneous Toeplitz (TOEPH) will be used. The Kenward-Roger method will be used to estimate the degrees of freedom. Type III tests for the least-squares means (LSM) will be used for the statistical comparison. The LSM difference, standard error, p-value and 100(1-alpha)% CI will also be reported.

Fisher's exact test will be used for the adverse events (AEs), discontinuation, and other categorical safety data for between-treatment group comparisons. Continuous vital signs, body weight, and other continuous safety variables, including laboratory variables, will be analyzed by an ANCOVA with treatment group and baseline value in the model. The significance of within-treatment group changes from baseline will be evaluated by testing whether or not the treatment group LSM changes from baseline are different from zero; the standard error for the LSM change will also be displayed. Differences in LSM will be displayed, with the p-value associated with the LSM comparison to placebo and a 95% CI on the LSM difference also provided. In addition to the LSMs for each group, the within-group p-value for the change from baseline will be displayed. Treatment-emergent high/low for categorical laboratory safety analyses will also be produced.

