## **6.4. Handling of Dropouts or Missing Data**

Missing data on the primary endpoint, HiSCR response, and other dichotomous endpoints will be imputed as nonresponse. As a supplementary analysis, the primary endpoint at week 16 will be imputed using the last observation prior to missingness. For other endpoints, including continuous secondary endpoints, missing data may be imputed using the last observation prior to missingness or other appropriate imputation methods.

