#### 6.7.3.2. Lesion Counts

The mean change from baseline to Week 16 for the total number of abscesses, inflammatory nodules, draining fistulae, and abscess and inflammatory nodule (AN) will be individually summarized and assessed using ANCOVA. Moreover, we will calculate the proportion of patients that achieve 50%, 75% and 90% decreases in AN count at W12 and W16. In addition to AN reduction, the proportion of patients with disease flare will be calculated up to W16, defined as a  $\geq 25\%$  increase in AN count from the baseline and  $\geq 2$  in AN count.

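### SAP 6.7.2 prescribes a log link for AN count although the endpoint is a mean change from baseline, and SAP 6.3.3 names MMRM as the main analysis without excepting the ANCOVA secondaries

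*SAP*

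**What the plan says.** - **SAP 6.7.2, endpoint.** "Secondary comparisons of interest are the mean change from baseline to Week 16 for" AN count and Skin Pain NRS.
- **SAP 6.7.2, model.** "An analysis of covariance (ANCOVA) model with proper link function will be used for analysis of these secondary endpoints", on both the mITT and per-protocol sets. For AN count it adds: "The AN count is a count data and we will use log transformation as the link function". It names no covariates, no response variable and no link for Skin Pain NRS, and does not say which analysis set is the main one.
- **SAP 6.7.3.2 (exploratory).** Change to Week 16 is listed again for several lesion counts. The list ends with "abscess and inflammatory nodule (AN) will be individually summarized and assessed using ANCOVA". No link is mentioned.
- **SAP 6.3.3.** "The main analysis for all continuous efficacy and health outcomes variables will use mixed model repeated measures (MMRM) analysis". No exception is stated.
- **Protocol 9.4.3.** "An analysis of covariance (ANCOVA) model will be used for analysis of these secondary endpoints". No link is mentioned.
- **SAP 6.4.** "For other endpoints, including continuous secondary endpoints, missing data may be imputed using the last observation prior to missingness", or by another appropriate method. This sentence also classes the secondaries as continuous.

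**The concern.** There are two separate problems.

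First, the AN-count model does not match the AN-count endpoint. The objective promises a mean change in lesions, and the prescribed link leads to a ratio or to a model that cannot be fitted sensibly. A programmer has to guess the response variable, how baseline enters and the scale of the result. The secondary result could then appear as a ratio under 6.7.2 and as a difference in lesions under 6.7.3.2.

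Second, for both AN count and Skin Pain NRS, the general methods section and the endpoint section name different main analyses. MMRM uses participants' earlier visits. A Week 16 ANCOVA depends on how missing Week 16 values are handled, and 6.4 leaves that open. If the choice is not written down before unblinding, it can be questioned afterwards.

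**Working it through.** No figure in the documents depends on this analysis. The only power statement is for HiSCR. The check is therefore a comparison of the text plus an illustration on assumed inputs.

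**Step 1: log link on the change.** A log link sets log(μ) = linear predictor, so μ = exp(linear predictor), which is always above 0. Entry requires an AN count of at least 4 (protocol 5.1, criterion 6), and improvement makes the change negative. Assume Week 16 counts average 45% of baseline on active and 70% on placebo. At a baseline mean of 11:
- active: (0.45 - 1) × 11 = -6.05
- placebo: (0.70 - 1) × 11 = -3.30

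Both means are negative, so neither can be represented. A trial fit to one simulated data set (15 placebo, 30 active, assumed inputs) bears this out. The Poisson log-link fit to change failed, and the Gaussian log-link fit returned coefficients of order 10^15 to 10^16.

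**Step 2: log link on the Week 16 count.** This can be fitted, but it estimates a ratio. Under the same assumption:
- ratio = 0.45 / 0.70 = 0.643 at every baseline
- difference in mean change = (0.45 - 0.70) × baseline mean

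| Assumed baseline mean | Ratio | Difference in mean change |
|---|---|---|
| 8 | 0.64 | -2.00 |
| 11 | 0.64 | -2.75 |
| 15 | 0.64 | -3.75 |

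One ratio corresponds to different mean changes. The SAP gives no step from the ratio to the stated endpoint.

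**Step 3: do the models disagree once put on one scale?** Simulation with complete data and assumed inputs: 34:17 and 42:21 participants; baseline AN of 4 plus a negative binomial count, overall mean 8, 11 or 15; negative binomial Week 16 counts with dispersion 0.5 or 1.0; 45% v 70% or 40% v 75% of baseline. Least-squares ANCOVA on change was compared with a quasi-Poisson log-link model of the Week 16 count on log baseline. After standardising the log-link fit to a mean difference, the average gap between the models was at most 0.10 lesions. The two tests fell on opposite sides of p = 0.05 in 4.6% to 10.6% of trials.

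**Step 4: ANCOVA or MMRM.**

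| Place | Endpoints | Method |
|---|---|---|
| SAP 6.3.3 | all continuous efficacy variables | MMRM |
| SAP 6.7.2, protocol 9.4.3 | AN count, Skin Pain NRS | ANCOVA |
| SAP 6.7.3.2 | lesion counts, including AN | ANCOVA |
| SAP 6.7.3.3, 6.7.3.4 | mSS, IHS4 | MMRM |
| SAP 6.7.3.5 | DLQI, Drainage NRS, Smell NRS | MMRM |
| SAP 6.7.3.5 | spinal pain scales | ANCOVA |

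Skin Pain NRS is missing from the MMRM list in 6.7.3.5 although it is patient-reported. Section 6.3.3 therefore behaves like a default that specific sections override. Its wording covers all such variables, however, and no precedence rule is written.

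**The case against.** The best reply on the log link is that the SAP attaches it to the AN count itself, described as count data, so a model of the Week 16 count is meant. Such a model is valid. This stands: it would be wrong to infer that the planned analysis cannot be run. It does not remove the mismatch, because the result is still a ratio while the endpoint is a mean change.

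A reader might also infer that 6.7.3.2 specifies a second, identity-link model for the same quantity. The text does not support that. It says ANCOVA and is silent on the link, and 6.7.2 uses ANCOVA for a model with a link. What can be said is that AN change is listed twice and that whether the log link carries over is not stated.

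On MMRM, the reply is that specific text overrides general text, and the pattern in Step 4 agrees. That largely stands. Protocol 9.4.4.1 states that "mixed-effects model of repeated measures (MMRM) will be the primary method of analysis for continuous endpoints", but it sits under the exploratory endpoints and does not govern the secondaries. What remains is the missing exception.

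Finally, a reader might infer that ANCOVA has to impute everyone without Week 16 data, and might attach a definite size to the gap between ANCOVA and MMRM. Section 6.4 only says that values may be imputed, and ANCOVA can be run on observed cases. Any such size would rest on an imputation rule, visit trajectory and correlation that the documents do not give.

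**Conclusion.** The concern holds as a specification defect in the secondary analyses and should be fixed before unblinding. As written, 6.7.2 does not deliver the stated AN-count endpoint on either reading of the link, and 6.3.3 lacks an exception for endpoints assigned to ANCOVA.

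The size is modest. The illustration rests wholly on assumed AN counts, and its close agreement on a common scale shows that the fault lies in the unstated response and effect measure, not in count models as such. The share of simulated trials with split test results shows only that the choice should be fixed in advance. The documents do not support any inference that the primary HiSCR analysis or the sample size is affected. These are secondary endpoints with no power claim and no multiplicity adjustment.

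**What to change.** 1. **SAP 6.7.2.** State that change from baseline to Week 16 in AN count and in Skin Pain NRS is analysed by identity-link ANCOVA with treatment and baseline value, on mITT, as the main analysis. This matches the endpoint and protocol 9.4.3. Move any log-link model of the Week 16 count to a supportive analysis, reported as a ratio or standardised to a mean difference.
2. **SAP 6.3.3.** Add to the MMRM sentence: *unless otherwise specified in Section 6.7*. A general clause is needed. An exception naming only 6.7.2 would imply MMRM for the other ANCOVA endpoints in 6.7.3.2 and 6.7.3.5. Keep MMRM as supportive for the two secondaries.
3. **SAP 6.7.3.2.** Remove AN change from the list or cross-refer it to 6.7.2.

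The cost is SAP wording only, with no protocol change. The downside is that the ANCOVA result depends on how missing Week 16 values are handled under 6.4. Protocol 9.2 expects about 45 of 63 randomised participants to complete the 16 weeks, so up to 63 - 45 = 18 (28.6%) could lack Week 16 data. On the SAP 6.2 figures it would be 51 - 45 = 6 (11.8%). The supportive MMRM makes that dependence visible.

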### 6.7.3. Exploratory Endpoints

#### 6.7.3.1. Additional HiSCR Response Definitions

The primary endpoint will be assessed using different definitions of HiSCR response at Week 16. Specifically, the needed reduction in AN count will be modified from 50% to 75% and to 90%. The same analysis method used for the primary endpoint will be used for these exploratory analyses. The percentage of responders achieving, HiSCR50, HiSCR75, and HiSCR90, in the mITT and the PPS population will be summarized by visit and by treatment arm to which the patients were randomized at Week 0 (Visit 2). A plot of the percentage of responders over weeks will be provided.

The proportion of visits that a patient achieves HiSCR response out of the total visits the patient attends during study period 1 and 2 (Week 0 to Week 36) will be calculated as follow,

$$\frac{\text{\# of visits the patient achieves HiSCR response}}{\text{Total \# of visits the patient attends}} * 100.$$

The HiSCR response is defined in Section 6.7.1 which is based on a patient's baseline values. The summary statistics of the proportion of visits achieving responses will be summarized by treatment arms to which the patients were randomized at Week 0 (Visit 2).

Moreover, the restricted mean response time (RMRT), a measure of the average time a responder stays a responder within a specified time period, will be provided up for responders at week 16 up (Visit 10) to week 36 (Visit 20) in each treatment arm, respectively. The time to loss of response in HiSCR50 is defined as  $\geq 50\%$  increase in AN compared to the average AN count from the 3 previous visits, and the increase was  $\geq 3$  AN from the average AN count of the 3 previous visits. Specifically, the RMRT is calculated as,

$$\sum_{k=10}^{20} \left\{ \prod_{v=10}^k \left( 1 - \frac{\delta_v}{R_v} \right) \right\} \times 2 \text{ weeks}$$

Where  $\delta_v$  is the number of patients who are responder at Visit 10 (week 16) but first loss response at Visit  $v$  and  $R_v$  is the number of patients who are responder at Visit 10 (week 16) and stay reponse before Visit  $v$ . The average RMRT will be summarized by treatment arm to which the patients were randomized at Week 0 (Visit 2).

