Table 3. Schedule of activities for the Post-Treatment Follow-Up Period of Study I7P-MC-DSAD For procedures at an early termination visit, see ETV in Table 2. For procedures at an unscheduled visit, see V997 in Table 2. Unscheduled visits are only for participants needing rescue therapy or incision and drainage. V802 Visit number V801 **Comment** 40 or 46 or Week relative to randomization ETV+4 ETV+10 323 Study day 281 Visit interval tolerance (days) ±7 ±7 Fasting visit No fasting in this period. X Concomitant medications X X X For AESIs, additional data are collected (Section 8.3.6). Adverse events Surgical interventions related to HS X X **Physical Evaluation** Blood pressure, body temperature, pulse rate. Vital signs should be measured after X X participant has been sitting for at least 5 minutes. Vital signs Symptom-directed physical examination X X See Section 8.2.2. **Patient-Reported Outcomes (Electronic)** Skin Pain - HS NRS X X X X Drainage NRS X Smell NRS X Patient's Global Impression of Severity – X 7 Days (Hidradenitis Suppurativa) X **Patient-Reported Outcomes (Paper)** Spinal Pain NRS Χ See Section 8.1.8. **Clinician-Administered Questionnaires (Electronic)** Lesion assessments Χ Χ Includes anatomical region, type and number (see Section 8.1.1). Clinician-Administered Questionnaires (Paper) C-SSRS Since Last Visit X X Self-Harm Supplement Form X X Χ Self-Harm Follow-Up Form Χ Required if triggered by the Self-Harm Supplement Form per instructions. **Laboratory Tests and Sample Collections** Hematology X X

X

X

Clinical chemistry

Table 3. Schedule of activities for the Post-Treatment Follow-Up Period of Study I7P-MC-DSAD

For procedures at an early termination visit, see ETV in Table 2.

For procedures at an unscheduled visit, see V997 in Table 2. Unscheduled visits are only for participants needing rescue therapy or incision and drainage.

Visit number	V801	V802	Comment
	40 or	46 or	
Week relative to randomization	ETV+4	ETV+10	
Study day	281	323	
Visit interval tolerance (days)	±7	±7	
Fasting visit			No fasting in this period.
			Only for WOCBP (Section 8.2.5.1 and Appendix 10.4) and women with a history of
Urine pregnancy (local)	X	X	tubal ligation.
C-reactive protein, high-sensitivity (hs-CRP)		X	
			If a hypersensitivity event occurs, collect additional samples (see Appendix 10.2,
Pharmacokinetic (PK) sample X		X	Section 10.2.2).
			If a hypersensitivity event occurs, collect additional samples (see Appendix 10.2,

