4.2. Scientific Rationale for Study Design

The primary endpoint of this study is the proportion of patients achieving Hidradenitis Suppurativa Clinical Response (HiSCR) at Week 16. HiSCR is defined as at least a 50% reduction in the total abscess and inflammatory nodule count (AN count) with no increase in abscess count and no increase in draining fistulae count relative to baseline. HiSCR has been used in previous HS trials and has been accepted by the Food and Drug Administration as a primary endpoint (Kimball et al. 2014; Kimball et al. 2016a; Kimball et al. 2016b). Evaluation of the primary endpoint at the Week 16 time point is appropriate based on current clinical trials of systemic immunomodulatory therapies in HS (guselkumab NCT03628924, secukinumab NCT03713632 and NCT03713619; bimekizumab NCT04242498 and NCT04242446).

A double-blind, placebo-controlled design through the first treatment period limits bias for the participant and investigator assessments and enables a clearer interpretation of the effects of active drug.

The second treatment period (open-label) allows for evaluation of both safety and changes in efficacy over time in participants who received LY3041658 in the placebo-controlled treatment period. The second treatment period also allows participants who were randomized to placebo in the first treatment period to receive LY3041658 in the open-label period for a treatment duration similar to that of the placebo-controlled period.

The post-treatment follow-up period allows for continued safety monitoring after the last dose. The last dose is given at Week 34. This is 2 weeks before the last visit in the second treatment period (Week 36) and a total of 12 weeks before the last post-treatment follow-up visit (Week 46). LY3041658 concentrations are expected to be significantly decreased in the plasma after 5 half-lives. The terminal half-life of LY3041658 is approximately 2 weeks, based on pharmacokinetic (PK) data from the Phase 1 Study DSAB. Therefore, for the present study, the planned duration of safety follow-up is adequate, as this duration covers approximately 6 half-lives. A follow-up period of a similar duration was used after the last dose of LY3041658 in the single-dose Study DSAA and multiple-dose Study DSAB.

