## 5. Study Design

### 5.1. Summary of Study Design

Study I7P-MC-DSAD (DSAD) is a multicenter, randomized, double-blind, placebo-controlled, parallel-group Phase 2 study to evaluate the efficacy and safety of LY3041658 600 mg given intravenously (IV) every 2 weeks (Q2W) in adults with HS.

The study duration will be up to approximately 51 weeks over 4 study periods:

Screening: a period lasting up to 35 days before Week 0 (Visit 2, baseline)

Treatment Period 1: a 16-week, 2-group double-blind treatment period:

- At baseline (Visit 2, Week 0), eligible participants will be randomized in a 2:1 ratio to receive either LY3041658 600 mg IV Q2W or placebo IV Q2W, starting at the baseline visit.

Treatment Period 2: a 20-week, single-group open-label extension period:

- Starting at Week 16, all participants, including those previously assigned to placebo, will receive LY3041658 600 mg IV Q2W until the last dosing visit.

Post-treatment follow-up: a period lasting approximately 10 weeks.

- Participants will not receive study drug in this period.
- The last dose of the study drug is given at Visit 19 (Week 34). Thus, participants will have been withdrawn from study drug for a total of 12 weeks at the last post-treatment follow-up visit (Visit 802, Week 46).

Approximately 76 patients will be screened to achieve approximately 51 participants randomized in a 2:1 ratio to one of two treatment groups:

[figure not shown]
approximately 34 participants randomized to LY3041658, and

approximately 17 participants randomized to placebo.

Unscheduled visits are for participants needing rescue therapy or incision and drainage. The use of concomitant medications, including rescue therapy, is described in Section 6.5 in the protocol.

Participants who permanently discontinue the study drug early (Section 7.1 in the protocol) will undergo early termination procedures, including an early termination visit (ETV) and the post-treatment follow-up visits specified in the Schedule of Activities (SoA) (Section 1.3 in the protocol).

Figure DSAD.5.1 illustrates the study design. The blinding procedure is described in the protocol.

**Figure DSAD.5.1. Schema of Study I7P-MC-DSAD, a Phase 2 study to evaluate the efficacy and safety of LY3041658 in adults with moderate-to-severe hidradenitis suppurativa.**

Note: Starting at Week 16 participants who received placebo in Treatment Period 1 will receive LY3041658 600 mg IV Q2W.

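### The restricted mean response time formula in SAP 6.7.3.1 adds eleven 2-week terms over a 20-week window, so it can return 22 weeks

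*SAP*

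**What the plan says.** SAP 6.7.3.1 introduces RMRT as "a measure of the average time a responder stays a responder within a specified time period". It sets the population and the period: the measure "will be provided up for responders at week 16 up (Visit 10) to week 36 (Visit 20) in each treatment arm".

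The formula is an outer sum over k = 10 to 20 of the product, over v = 10 to k, of (1 − δ_v / R_v), times 2 weeks. Here δ_v "is the number of patients who are responder at Visit 10 (week 16) but first loss response at Visit" *v*, and R_v counts the Visit 10 responders still in response before Visit *v*.

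Reporting is descriptive: "The average RMRT will be summarized by treatment arm to which the patients were randomized at Week 0 (Visit 2"). The SAP plans no test or contrast for RMRT.

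The length of the window is confirmed elsewhere. SAP 5.1 lists "Treatment Period 2: a 20-week, single-group open-label extension period". The schedule of activities (Protocol 1.3, Tables 1 and 2) puts Visit 10 at Week 16 and Visits 11 to 20 at Weeks 18 to 36, two weeks apart.

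**The concern.** Visits 10 to 20 are eleven visits but only ten intervals. The outer sum gives every visit a 2-week interval, so it contains one interval more than the window holds. A programmer who follows the formula literally will overstate the mean time in response.

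The error would not always be visible. A value above 20 weeks would show that something was wrong, but in most data the result would stay below 20 and look admissible while still being too high. The excess also depends on how many patients remain in response, so it need not be the same in the two arms. A reader who sets the two averages side by side could see a gap that is partly produced by the formula.

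**Working it through.** **Inputs**
- Window: Week 16 (Visit 10) to Week 36 (Visit 20), from SAP 6.7.3.1.
- Visit spacing: 2 weeks, from Protocol 1.3, Tables 1 and 2.
- Formula: SAP 6.7.3.1. Write S(k) for the product through Visit k.
- Loss rates: none are given in the documents. The rates below are assumptions.

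**Step 1: the window.** 36 − 16 = 20 weeks, and 20 / 2 = 10 intervals. This agrees with the Treatment Period 2 length in SAP 5.1.

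**Step 2: the printed formula with no losses.** Every δ_v is 0, so every S(k) is 1. The number of terms is 20 − 10 + 1 = 11, and 11 × 1 × 2 = 22 weeks. That is 2 weeks, or 10%, over the 20-week ceiling. Placing the 2 weeks inside or outside the sum makes no difference.

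**Step 3: which term is surplus.** δ_v records first loss at Visit v, and R_v counts those in response before Visit v. The product is therefore a step curve that drops at the visit, and S(k) holds from Visit k until the next visit. The k = 10 term covers Weeks 16 to 18 and the k = 19 term covers Weeks 34 to 36. The k = 20 term covers Weeks 36 to 38. Protocol 4.2, describing the last dose, confirms where the period ends: "This is 2 weeks before the last visit in the second treatment period (Week 36"). Table 3 puts the next scheduled visit at Week 40. So the k = 20 term lies outside the window.

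**Step 4: the size.** Printed value − correct value = 2 × Σ S(10..20) − 2 × Σ S(10..19) = 2 × S(20).

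For a constant loss h per visit from Visit 11, S(k) = (1 − h)^(k − 10), and the excess is 2 × (1 − h)^10:

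| Assumed loss per visit | Printed, k = 10 to 20 (weeks) | k = 10 to 19 (weeks) | Excess (weeks) |
|---|---|---|---|
| 0% | 22.00 | 20.00 | 2.00 |
| 2% | 19.93 | 18.29 | 1.63 |
| 5% | 17.25 | 16.05 | 1.20 |
| 10% | 13.72 | 13.03 | 0.70 |
| 20% | 9.14 | 8.93 | 0.21 |

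Differences are taken before rounding. Under constant loss, the printed value passes 20 weeks only when the loss is below about 1.9% per visit, with about 82% still in response at Week 36.

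**Step 5: the lower limit.** If every responder loses response at Visit 20, S(20) = 0, both sums give 20.00 and the excess is 0. If all lose response at Visit 11, both give 2.00 and the excess is again 0.

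**Step 6: two arms side by side.** For assumed losses of 5% in one arm and 10% in the other, the printed difference is 17.248 − 13.724 = 3.524 weeks. With k = 10 to 19 it is 3.024 weeks. The distortion is 1.197 − 0.697 = 0.500 weeks.

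**The case against.** **The consequence is small.** RMRT is one exploratory summary, restricted to Week 16 responders, in a period when both arms receive the same drug. No test or decision depends on it. This is correct, and it is why the point is minor. It does not make the formula right.

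**22 weeks is an edge case.** It needs an arm with no losses, and every other figure rests on assumed rates. This also stands. The defect itself needs no assumed rate: eleven 2-week terms cannot fit in 20 weeks.

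**Each term might cover the interval ending at Visit k.** The surplus term would then be k = 10, crediting Weeks 14 to 16. A reader might infer from this that every reported RMRT is a flat 2 weeks too long. That is not the natural reading, because losses are defined as occurring at the visit and the risk set as standing just before it. A flat 2 weeks would also require that no loss be recorded at Visit 10. Under that reading the error would cancel between arms, but the extra interval would still fall outside the window.

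**The first factor need not be 1.** The loss rule looks at an "increase in AN compared to the average AN count from the 3 previous visits", not at baseline, so a Visit 10 responder could meet it at Visit 10. This is a fair caution about the assumed curves. It lowers S(20) in such data but does not remove the extra term. For example, with 10% lost at Visit 10 and none later, the printed sum is 19.8 weeks against 18.0.

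**Conclusion.** Wrong as written, minor. The outer sum has one term too many, and nothing else in the SAP or protocol corrects it. On the step-curve reading that the definitions imply, RMRT is overstated by 2 × S(20) weeks, between 0 and 2. That result needs only the SAP's definitions and the 2-week schedule. The figures of 1.63, 1.20, 0.70 and 0.21 weeks, and the 0.50-week arm distortion, are illustrations that assume constant losses from Visit 11.

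The documents do not support two wider inferences that a reader might draw. The first is that the reported value is undefined because no interval convention is stated. For given δ_v and R_v the printed formula returns a single number, and the convention matters only for saying what the number should have been. The second is that the trial's efficacy comparison is compromised. The plan only summarizes RMRT by randomized arm, with no contrast, and the formula does not enter the primary, secondary, safety or sample-size calculations.

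**What to change.** Change the upper limit of the outer sum from 20 to 19, so that ten terms give a maximum of 20 weeks. Leave the inner product as it is. Add one sentence to SAP 6.7.3.1 stating that each term covers the 2-week interval starting at Visit k.

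The cost is one summation limit in the SAP and in the program, plus that sentence. No new data are needed and no endpoint definition changes. A simple program check is to feed in a data set with no losses and confirm that the result is exactly 20 weeks.
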